I acknowledge that I am responsible for the overall study conduct and I agree to personally conduct or supervise the described clinical study.

I agree to ensure that the confidential information contained in this document will not be used for any purpose other than the evaluation or conduct of the clinical investigation without the prior written consent of GB004, Inc.

Signature

Name of Investigator

Date

PROTOCOL AMENDMENT SUMMARY OF CHANGES TABLE

DOCUMENT HISTORY	
Document	Date
Amendment 2.0 (v3.0)	15 December 2021
Amendment 1.0 (v2.0)	21 October 2020
Original Protocol (v1.0)	27 July 2020

Amendment 2.0 (v3.0, 15 December 2021)

Overall Rationale for the Amendment:

The purpose of this amendment is primarily to make updates to Section 6.8 (Concomitant Medications) and Appendix 6 (Prohibited Medications).

Table 1: Summary of Changes

Section # and Name	Description of Change	Brief Rationale
6.8 Concomitant Therapy	Guidance has been added regarding the use of sensitive clinical substrates of OCT2 and CYP2C8 with GB004.	Results from in vitro studies indicate that a glucuronide metabolite of GBD242, may be an inhibitor of OCT2 and CYP2C8.
Appendix 6	Added dofetilide and sensitive substrates of CYP2C8 to Prohibited Medications.	Concomitant use of dofetilide, which is contraindicated when used with OCT2 inhibitors, is prohibited in this study. Concomitant use of sensitive substrates of CYP2C8 (eg, repaglinide, rosiglitazone, pioglitazone, and loperamide) is prohibited in this study.
1.3.2 Open-Label Extension – Schedule of Activities	Added Physician's Global Assessment (PGA) at the OLE Follow-up visit.	This assessment should occur at the OLE Follow-up visit.
1.2 Study Schema	Edited text in study schema for consistency with protocol text.	For overall clarity and alignment with protocol text.
4.1.2 OLE (24 Weeks)	Added text “(if last dose of PCP IP has not been taken earlier in the day)” to the second sentence of the second paragraph.	The change was made for clarity.
5.2 Exclusion Criterion #22	Estimated glomerular filtration rate (eGFR) was corrected to read < 60 mL/min/1.73 m ² .	Change was made to correct an earlier oversight.

9.4.1.1 Efficacy Analysis, Secondary Endpoints	The second sentence was updated to read: Histologic remission at PCP Week 12 and mucosal healing at PCP Week 12 will be evaluated among subjects with Baseline lamina propria neutrophils and neutrophils in epithelium RHI subscores > 0.	Change was made to correct an earlier oversight.

1. PROTOCOL SUMMARY

1.1. Synopsis

Protocol Title: A Phase 2, randomized, double-blind, placebo-controlled, multi-center study to evaluate GB004 in adult subjects with mild-to-moderate active ulcerative colitis

Short Title: GB004 in adult subjects with active ulcerative colitis

Rationale

GB004 (formerly AKB-4924) is a novel small molecule in development for the treatment of inflammatory bowel disease (IBD). The novel approach of GB004 is based on evidence that hypoxia inducible factor 1 alpha (HIF-1 α), a member of the hypoxia inducible factor (HIF) transcription factor family, has a crucial role in the maintenance of epithelial barrier integrity and in the modulation of the innate inflammatory response in mouse models of IBD.

Small molecule prolyl hydroxylase inhibitors (PHDi's) stabilize HIF-1 α protein and have shown efficacy in multiple mouse models of IBD that include trinitrobenzene sulfonic acid (TNBS) and dextran sulfate sodium (DSS)-induced colitis models and the tumor necrosis factor alpha (TNF α)-driven terminal ileitis model (Ablin, 1999; Minaiyan, 2012). Prolyl hydroxylases (PHDs) are key regulators of the HIF pathway (Eltzschig, 2014). These findings support PHD inhibition as a target for treating ulcerative colitis (UC).

GB004, a HIF-1 α stabilizer, is being developed as an oral therapeutic, gut-targeted treatment for UC with higher intestinal than systemic exposure. The relatively low oral bioavailability (< 20%) and preferential distribution to the gastrointestinal (GI) tissues observed in nonclinical studies, combined with its mechanism of action in gut lumen and positive effects on gut healing and inflammation in animal models of colitis, provide rationale for further development in human subjects.

GB004 has been shown in studies of both healthy volunteers (AKB-4924-CI-1001, AKB-4924-CI-1002, and GB004-1902) and patients with UC (GB004-1101) to be a gut-targeted treatment with higher intestinal than systemic exposure. In addition, the GB004-1101 study, although limited by only 4 weeks of dosing, showed trends in improvement in clinical and histologic outcomes in UC patients. GB004, Inc. has developed tablet formulations with 2 release profiles, tablets and delayed-release (DR) tablets, which have distinct systemic profiles with both delivering GB004 to the colonic tissue.

This 2-part study, comprising of a 36-week placebo-controlled period and a 24-week open-label extension period, will assess the efficacy and safety of GB004 when added to background UC therapy of 5-aminosalicylate (5-ASA) with or without systemic steroids.

Objectives and Endpoints

Placebo-Controlled Period (PCP) (Primary, Secondary and Safety Objectives and Endpoints)

Objectives	Endpoints
Primary	

 To evaluate the effect of GB004 compared to placebo on clinical remission at PCP Week 12 	
 Proportion of subjects with clinical remission at PCP Week 12, defined as a Modified Mayo score ≤ 2, with a Rectal bleeding subscore of 0, Stool frequency subscore of 0 or 1 (with a ≥ 1 point decrease from baseline), and Endoscopic subscore of 0 or 1
Secondary	

 To evaluate the effect of GB004 on clinical response, histologic remission, endoscopic improvement, mucosal healing at PCP Week 12 	
 Proportion of subjects with clinical response at PCP Week 12, defined as reduction in the Modified Mayo score of ≥ 2 points and ≥ 35 percent reduction from baseline, including a decrease in Rectal bleeding subscore of ≥ 1 or absolute Rectal bleeding subscore of ≤ 1 Proportion of subjects with histologic remission at PCP Week 12, defined as Robarts Histopathology Index (RHI) ≤ 3 with lamina propria neutrophils subscore = 0 and neutrophils in epithelium subscore = 0 Proportion of subjects with endoscopic improvement at PCP Week 12, defined as endoscopic subscore of 0 or 1 Proportion of subjects with mucosal healing at PCP Week 12, defined as endoscopic improvement and histologic remission

 To evaluate the effect of GB004 on clinical remission, clinical response, histologic remission, endoscopic improvement, and mucosal healing at PCP Week 36 	
 Proportion of subjects with clinical remission at PCP Week 36 Proportion of subjects with clinical response at PCP Week 36 Proportion of subjects with histologic remission at PCP Week 36 Proportion of subjects with endoscopic improvement at PCP Week 36 Proportion of subjects with mucosal healing at PCP Week 36
Safety	

 To evaluate the safety and tolerability of GB004 	
 Incidence of treatment-emergent adverse events (TEAEs)

Open-Label Extension (OLE) (Primary)

Objectives	Endpoints
Primary	

To evaluate the safety and tolerability of GB004	
Incidence of TEAEs

Overall Design

This is a 2-part study in adult subjects with mild-to-moderate active UC who have disease activity despite treatment with 5-ASA with or without systemic steroids:

- The Placebo-Controlled period (PCP) is a randomized, placebo-controlled, multi-center, 36-week study evaluating the efficacy, safety, tolerability and pharmacokinetics (PK) of 2 dose regimens of GB004; the initial 12 weeks of treatment will be double-blind.
- The OLE is an open-label, multi-center, 24-week study evaluating the safety and tolerability of GB004 twice per day (BID) dose regimen

Subjects who complete the Week 36 visit on IP and subjects who meet the predefined UC Disease Activity criteria at or after PCP Week 12 visit and prior to PCP Week 36 visit on IP can enter the OLE (for details refer to Section [5.3](#)).

All subjects participating in the study will be required to maintain a stable dose of 5-ASA throughout the study. Subjects on systemic corticosteroids must remain on a stable dose during the initial 12 weeks of the PCP (for details refer to Section [6.5.2](#)). After the PCP Week 12 visit, a standardized taper from systemic corticosteroids may be attempted at any time.

All subjects will attend a Follow-up visit at the clinic 4 weeks after last dose of IP.

A data review committee (DRC) will periodically convene to review unblinded overall safety and emerging efficacy results (Section [9.5.1](#)).

A schematic of the study design is presented in Section [1.2](#).

Placebo-Controlled Period (36 weeks)

After signing an informed consent form (ICF), subjects will be screened for study eligibility over a Screening period of up to 5 weeks. During the Screening period, subjects will capture stool frequency and rectal bleeding symptoms in a provided electronic diary (eDiary) on a daily basis. Flexible sigmoidoscopy or colonoscopy will be performed at screening. Subjects not meeting the eligibility criteria will be deemed screen failures and will not continue participation in the study.

On Day 1/Week 0, eligible subjects will be randomized 1:1:1 to receive the following treatments for 36 weeks:

- GB004 480 mg BID
- GB004 480 mg once daily (QD)
- Placebo

Randomization will be stratified by systemic corticosteroid use at baseline (yes/no).

All subjects will dose investigational product (IP) BID to maintain the blind (for details refer to Section 6.1).

The first dose of IP will be administered in the clinic on Day 1/Week 0 with food. All subsequent doses will be taken at home with food with the exception of the morning doses at the Week 2, 4, 8, 12, and 36 visits where IP will be administered in the clinic, with food, after predose blood collection as specified in the Schedule of Activities (SoA) in Section 1.3.1 – PCP.

After initiation of IP on Day 1/Week 0, subjects will return to the clinic and will be evaluated as specified in the SoA, see Section 1.3.1. A flexible sigmoidoscopy with biopsies will be performed at the PCP Week 12 and Week 36 visits (and at an Unscheduled UC Disease Activity Criteria Assessment visit(s) and the Early Withdrawal from Study visit, if applicable).

OLE (24 weeks)

Subjects may participate in the 24-week OLE if in the opinion of the Investigator they have been compliant with study procedures and:

- Completed the Week 36 visit on IP; or
- Met the predefined UC Disease Activity criteria any time after PCP Week 12 visit and prior to PCP Week 36 visit on IP (refer to Section 5.3)

Beginning at the OLE Enrollment visit, all subjects will receive GB004 480 mg BID for 24 weeks. All doses will be taken at home with food with the exception of the morning dose at the OLE Enrollment visit, OLE Week 2, 12 and End of OLE visit/Early termination (ET) visit where IP will be administered in the clinic, with food, after predose blood collection as specified in the SoA (Section 1.3.2 – OLE). Subsequently, subjects will return to the clinic and be evaluated as specified in the SoA (Section 1.3.2 - OLE).

Number of Participants and Intervention Groups

The study will randomize approximately 195 subjects, with approximately 65 subjects per treatment group in the PCP.

[figure not shown]
Duration

Total duration for study participation per subject is as follows:

Study period	PCP	OLE
Screening period:	up to 5 weeks	Not applicable
Treatment period:	up to 36 weeks	24 weeks
Follow-up period:	4 weeks after last dose of IP	

Data Review Committee: Yes

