1.3.2. Open-Label Extension - Schedule of Activities

OLE Procedure	OLE Enrollment visit (same as PCP last visit)*	Treatment Period			Follow-up (+4 weeks after last dose of IP)	Notes *Assessments completed within 14 days of PCP last visit will not be required to be repeated during the OLE Enrollment visit
				End of OLE / ET		
Visit	201	202	203, 204, 205, 206,	207	208 + 4 weeks from End of OLE/ET	Some visits/study procedures may be done via virtual visits or at home visits. Refer to Appendix 9 and the Study Reference Manual for more details on guidance for global health emergencies.
OLE Week	0/D1	2	4, 8, 12, 18	24		
Window (days)		±3	±3	±3	±3	
Hematology with differential	X	X	X	X	X	See Appendix 2 for details.
Clinical chemistry	X	X	X	X	X	See Appendix 2 for details. Note, inclusive of CRP.
Urinalysis	X			X	X	See Appendix 2 for details.
Pregnancy test	X		U	S	S	Serum (S), Urine (U)
			Monthly ^a			a. with a provided at-home urine pregnancy kit to be done in between clinic visits; if urine test is positive, subject must discontinue IP and return for confirmatory serum pregnancy test.
Concomitant medications	X	X	X	X	X	
Adverse events	<===== X =====>					
Complete physical exam				X		Refer to Section 8.2.1
Vital Signs	X	X	X	X	X	Includes weight
12-lead electrocardiogram			Week 12	X	X	
Review eDiary		X	X	X		
Physician's Global Assessment (PGA)	X	X	X	X	X	
Blood for serum markers	X		Week 12	X		Collected predose (morning) Serum markers include, but not limited to: iron, transferrin, total iron binding capacity, serum ferritin, hepcidin, zinc
Blood for plasma markers	X		Week 12	X		Collected predose (morning) on dosing days: EPO and VEGF

OLE Procedure	OLE Enrollment visit (same as PCP last visit)*	Treatment Period			End of OLE / ET	Follow-up (+4 weeks after last dose of IP)	Notes *Assessments completed within 14 days of PCP last visit will not be required to be repeated during the OLE Enrollment visit
Visit	201	202	203, 204, 205, 206,	207	208	+ 4 weeks from End of OLE/ET	Some visits/study procedures may be done via virtual visits or at home visits. Refer to Appendix 9 and the Study Reference Manual for more details on guidance for global health emergencies.
OLE Week	0/D1	2	4, 8, 12, 18	24			
Window (days)		±3	±3	±3	±3		
PK blood sample		X ^b					b. PK samples to be collected at predose, 0.5, 2 and 4 hours postdose
Stool sample (PD)	X			X			See Section 8.5 for details
Dispense IP	X	X	X				

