4.1.2. OLE (24 weeks)

Subjects may participate in the 24-week OLE if in the opinion of the Investigator they have been compliant with study procedures and:

- Completed the Week 36 visit on IP; or
- Met the predefined UC Disease Activity criteria any time after PCP Week 12 visit and prior to PCP Week 36 visit on IP (refer to Section 5.3)

Beginning at the OLE Enrollment visit, all subjects will receive GB004 480 mg BID for 24 weeks. All doses will be taken at home with food with the exception of the morning dose at the OLE Enrollment visit (if last dose of PCP IP has not been taken earlier in the day), OLE Week 2, 12 and End of OLE visit/Early termination (ET) visit where IP will be administered in the clinic, with food, after predose blood collection as specified in the SoA (Section 1.3.2 – OLE).

Subsequently, subjects will return to the clinic and be evaluated as specified in the SoA (Section 1.3.2 - OLE).

Consideration should be given to discontinuing IP for subjects who do not show clinical improvement per Investigator's judgement by OLE Week 12. Subjects who permanently discontinue IP during the OLE will be withdrawn from the study, complete the End of OLE/ET visit and will be asked to return for a Follow-up visit approximately 4 weeks after their last dose of IP to assess safety.

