6.4. Investigational Product Compliance

The first dose of IP will be administered in the clinic on PCP Day 1/Week 0 with food. All subsequent doses will be taken at home with food with the exception of the morning doses at the PCP Week 2, 4, 8, 12, and 36 visits and OLE Enrollment, Week 2, 12 and EOT visits where IP will be administered in the clinic, with food, after pre-dose blood collection as specified in the SoA (Section 1.3.1 – PCP and Section 1.3.2 – OLE).

After initiation of IP on PCP Day 1/Week 0 visit, subjects will visit the clinic for assessments of IP use as specified in the SoA (Section 1.3.1 – PCP and Section 1.3.2 – OLE). IP accountability will be assessed by counting returned tablets. Subjects who demonstrate poor IP compliance should be re-educated on the importance of taking their medications as prescribed.

Subjects will be asked to record dosing information on a daily basis in an eDiary.

For additional details refer to Study Reference Manuals.

Guidance for Missed Dose(s)

If a dose is missed, subjects should be instructed to skip the missed dose if there are less than 6 hours before the time of the next dose, resume dosing at their next scheduled dosing time, and document the missed dose.

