6.7. Treatment of Overdose

Any dose of IP greater than the prescribed daily dose within the same calendar day will be considered an overdose.

There is no specific treatment recommended to treat an overdose of IP and the subject should receive treatment directed towards any symptoms manifested.

In the event of an overdose, the Investigator should:

- Contact the Sponsor's Medical Monitor (or designee) as soon as possible.

- Closely monitor the subject for any AE/SAE and laboratory abnormalities.
- Document the quantity of the excess dose as well as the duration of the overdose in the electronic case report form (eCRF).

Decisions regarding dose interruptions will be made by the Investigator in consultation with the Sponsor's Medical Monitor (or designee) based on the clinical evaluation of the subject.

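### Protocol sections disagree on whether the clinic morning dose at OLE Enrollment is conditional, leaving room for two morning doses on the transition day

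*Protocol*

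**What the plan says.** Four current places in the protocol bear on dosing on the day a subject moves from the PCP to the OLE.

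- **Synopsis (Section 1.1).** The PCP paragraph moves to the clinic the "morning doses at the Week 2, 4, 8, 12, and 36 visits where IP will be administered in the clinic, with food". The OLE paragraph has all doses at home "with the exception of the morning dose at the OLE Enrollment visit, OLE Week 2, 12" and the final OLE visit. Neither carries a condition.
- **Section 6.4.** One sentence covers both periods and lists clinic dosing for the "morning doses at the PCP Week 2, 4, 8, 12, and 36 visits and OLE Enrollment, Week 2, 12 and EOT visits", again without a condition.
- **Section 4.1.2.** The same rule appears with a restriction: "morning dose at the OLE Enrollment visit (if last dose of PCP IP has not been taken earlier in the day").
- **OLE Schedule of Activities (Section 1.3.2).** The first column is headed "OLE Enrollment visit (same as PCP last visit"). A note waives repeat assessments if they were done within 14 days of the last PCP visit, so some gap is foreseen.

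Three other provisions matter. Section 6.1 (Table 3) sets a dose at 4 tablets plus 4 delayed-release tablets of 60 mg, with doses roughly 8 to 12 hours apart. The Synopsis and Section 4.1.2 start 480 mg BID at the Enrollment visit. Section 6.7 states: "Any dose of IP greater than the prescribed daily dose within the same calendar day will be considered an overdose".

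**The concern.** When Enrollment and the last PCP visit are one visit, the Synopsis and Section 6.4 list a clinic morning dose under each period for the same morning. Only Section 4.1.2 says what to do when a PCP dose has already been taken. Section 6.4 covers dosing compliance and missed doses, so site staff may well work from it and never see the condition.

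What is at stake is dosing on one day for each subject who enters the OLE on the day of the last PCP visit. A subject could receive two doses in one morning and then the evening dose of the new regimen. Section 4.3 treats 480 mg BID as the highest dose in the study and rests its safety-margin argument on that regimen, so the instruction for this day should not depend on which section a site opens.

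**Working it through.** **Inputs.** Tablet strength 60 mg; 8 tablets per dose; active drug in the morning dose of both GB004 arms; 8 placebo tablets in the placebo arm (all Section 6.1, Table 3). OLE regimen 480 mg BID from Enrollment (Section 4.1.2). I assume full, unreduced dosing, Enrollment on the day of the last PCP visit, and an OLE evening dose that day where shown.

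**The plan's own figure.** (4 + 4) × 60 mg = 480 mg per dose. Twice daily: 2 × 8 = 16 tablets, 2 × 480 = 960 mg. This reproduces the stated dose.

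**Transition day, by former PCP arm (tablets of investigational product; mg of GB004).**

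| PCP arm | PCP morning + OLE evening (Section 4.1.2 condition applied) | PCP morning + OLE morning, no evening dose | PCP morning + OLE morning + OLE evening |
|---|---|---|---|
| BID | 16; 480 + 480 = 960 | 16; 480 + 480 = 960 | 24; 480 + 480 + 480 = 1,440 |
| QD | 16; 480 + 480 = 960 | 16; 480 + 480 = 960 | 24; 480 + 480 + 480 = 1,440 |
| Placebo | 16; 0 + 480 = 480 | 16; 0 + 480 = 480 | 24; 0 + 480 + 480 = 960 |

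**Spacing.** Two doses that both fall before noon are less than 8 hours apart unless the first is taken by 04:00 (12:00 − 8 h). Two morning doses would therefore ordinarily break the Section 6.1 interval in every arm, whether or not an evening dose follows.

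**Daily total.** Two morning doses equal the 16-tablet day and do not exceed it. The excess, 24 − 16 = 8 tablets, appears only when the evening dose is also taken.

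**Where the first dose is taken.** Among possible transition visits, a PCP clinic dose is specified only at Weeks 12 and 36. For entry at Week 18, 24 or 30 or at an unscheduled visit, the PCP morning dose would be taken at home. The duplication there would be a home dose followed by an unconditional clinic Enrollment dose.

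**Data handling.** SAP Section 7.1 has a rule for a last PCP dose and first OLE dose on the same date (the day counts as 0.5 of a PCP day). SAP Section 3.1.2 cuts PCP data at the date and, where ascertainable, time of the first OLE dose. SAP Section 9.1 assigns adverse events by the first OLE dose and falls back on the eCRF used when times are missing.

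**The case against.** The best defence is that the Synopsis and Section 6.4 mainly say where doses are taken. They list visits at which the morning dose moves from home to clinic, and neither tells a site to give a PCP morning dose and then an OLE one. The regimen comes from Section 6.1: twice daily, hours apart. On that reading a shared visit has one morning dose, and both lists merely place it in the clinic. Section 4.1.2, the dedicated OLE section, then supplies the explicit rule.

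Much of this stands. Duplicate dosing is a possible misreading and not something the protocol orders. But the sentences also say that product will be administered in the clinic at those visits. One section has a condition that the other two lack, and a site should not have to infer it.

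A reader might infer three stronger points, none of which the documents support:

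- **That the overdose definition is itself contradicted.** It is not. Two morning doses stay at the daily count. If the text really did prescribe three doses, one could argue that the prescribed amount was not exceeded.
- **That all of about 195 subjects are exposed to 1,440 mg.** Section 9.2.2 gives that number only as a ceiling on OLE entry. With 1:1:1 allocation, one third are assigned to placebo and would reach 960 mg at most. The 14-day note also means same-day enrollment is the default and not universal.
- **That attribution of exposure or adverse events between periods is left undefined.** The SAP's same-day rules already cover it.

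**Conclusion.** The inconsistency holds, in limited form. Current sections differ on whether the OLE Enrollment clinic dose depends on an earlier PCP dose that day. Followed literally, the unconditional wording could lead to two morning doses, which would ordinarily conflict with Section 6.1 spacing. With an evening dose as well, the total is 24 tablets against 16, which could meet the Section 6.7 definition of overdose. The 1,440 mg figure requires same-day enrollment, both morning doses, the evening dose, full dosing, and active drug in the PCP morning dose. The documents do not say how many subjects would meet these conditions.

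This is an inconsistency in operative dosing text that should be corrected. It has no bearing on endpoints, sample size, power or error rates. The conclusion compares current sections with each other and does not rely on the amendment summary.

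**What to change.** Reconcile the Synopsis (OLE paragraph), Section 6.4, Section 4.1.2 and the OLE Schedule of Activities so that all four give the same instruction for the transition day. It should cover entry at Weeks 12 and 36, where a PCP clinic dose is listed, and entry at other visits, where the PCP dose would be taken at home. The sponsor's clinical team decides which wording stands; this review takes no position on the dosing rule.

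The cost is a protocol clarification or a memo to sites. No change to the SAP is needed.
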